neonatal deaths despite being resuscitated. A potential way of improving maternal and perinatal outcomes among women with OL would be to buffer the excess lactic acid with sodium bicarbonate, achieving intrauterine resuscitation whilst awaiting an emergency cesarean section. However, in this situation, there is inadequate time (or staff) to correct the acidosis through careful titration of the bicarbonate infusion. A universal safe and effective dose would therefore facilitate its use. In our previous RCT, a single dose of 4.2g was insufficient to achieve changes in maternal or neonatal lactate levels. It is not known if a higher dose of bicarbonate would reverse the acidosis and achieve clinical benefits for the mother and baby. Therefore, we propose to undertake a placebo-controlled, dose-ranging pilot trial to determine the efficacy and safety of a preoperative infusion of sodium bicarbonate on acidosis, compared with placebo among women with obstructed labour (OL).

Justification

Undertaking a placebo-controlled, dose-ranging pilot trial shall establish a universal safe and effective dose of sodium bicarbonate for use to correct the acidosis among women with obstructed labour. Our results will inform the design of a full-scale effectiveness phase III trial to determine the effect of this preoperative infusion on maternal and perinatal outcomes. Furthermore, this information will facilitate the inclusion of sodium bicarbonate infusion in the standard preoperative preparation for women with obstructed labour in a low resource setting.

Objectives

General objective

To determine the efficacy and safety of a preoperative infusion of sodium bicarbonate on pH and lactate levels (metabolic acidosis) among women with obstructed labour.

Specific objectives

1. To determine the efficacy of a preoperative infusion of sodium bicarbonate on acidosis, compared with placebo among women with obstructed labour (OL).
2. To determine the safety of a preoperative infusion of sodium bicarbonate compared with placebo among women with obstructed labour (OL).

Hypothesis

We hypothesize that a higher dose of bicarbonate can safely lower the lactate levels (metabolic acidosis) by at least 20%.

Methods and materials

Study design

We will conduct a dose-finding phase III, randomized, double-blind, placebo-controlled, parallel-group trial.

Study setting

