Randomisation: A sequence of random numbers will be generated by an independent biostatistician using an online randomization service at www.sealedenvelope.com in permuted block sizes of four, six and eight. An independent, off-site pharmacist will prepare and consecutively number identical study packages using

the generated random numbers. This will ensure that the allocation is concealed. At the study site, after gaining consent, the research midwife will take the next sequentially labeled study drug package and administer its contents to the eligible participant. Therefore, both the participants and data collectors will remain blinded throughout the study.

Intervention/ Comparator: Eligible participants will be randomly assigned to receive 100 mls (8.4g), 150 mls (12.6g) and 200 mls (16.8g) of 8.4% sodium bicarbonate solution, or placebo (50 mls of NS 0.9%) in a ratio of 1:1:1:1. The study drug (Sodium Bicarbonate 8.4% and Normal Saline 0.9%) will be contained in identical 25 mL glass vials (Neon Laboratories Ltd, Mumbai, India), administered intravenously as a single bolus dose. Since the average waiting time for CS in our labour ward is approximately 110 minutes [11], there will be no need for a repeat dose.

In addition, all patients will receive the available Ministry of Health recommended standard preoperative care for all patients with OL which includes antibiotic prophylaxis, intravenous fluid replacement (1.5 L of normal saline), bladder drainage and lying in left-lateral position as they are being prepared for caesarean section [23]. Details in flow diagram 1.

Data collection

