Our research assistants will be qualified midwives with training in data collection, using dedicated password protected android devices. We will also review relevant health facility records such as antenatal care cards, case notes/file, the maternity and theatre registers. Laboratory parameters including lactate will be measured at baseline, and every thirty minutes after study drug administration until delivery to obtain samples for lactate measurement in umbilical cord blood and the myometrium. The participants will be followed for 7 days postnatal to ascertain the secondary perinatal outcomes and for 14 days postpartum to determine the secondary maternal outcomes. In the first 24 hours after study drug administration, the participants will be closely monitored to identify any drug reactions/adverse events. After administration of the study drug, all the participants will be actively monitored by a research midwife up to 24 hours. The women will be examined and asked directly about the presence of side effects.

Sample collection quality control

Qualified and well-trained research midwives will draw five millilitres (ml) of blood by venipuncture at the antecubital fossa of the non- dominant arm from each participant using a five millilitres syringe. After removing the epidermal needle and the tops of the vacutainers, two millilitres will be emptied into a purple top vacutainer for a full blood count, blood grouping and cross-matching as part of the standard preoperative preparation for all patients with obstructed labour in the hospital. The remaining three millilitres will be emptied into a red top vacutainer for blood chemistries including electrolytes, these are not part of the routine preoperative preparation for patients before caesarean section. Each blood sample will be transported to the laboratory in an ice-cooled container within 30 minutes of collection. Urine samples: Mid-stream urine, ten millimeters will be collected in sterile urine container from the mothers. We will monitor strict adherence to the standard operating procedures for collecting and handling participant samples through ongoing training and spot checks.

Cord blood collection

After the baby is born, the midwife will double clamp and cut the umbilical cord. Cleanse a 4" - 6" area of the umbilical cord with alcohol to remove maternal blood and contaminants (before the delivery of the placenta, if possible). Then blood will be drawn from the cord with a needle.

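### The four arms receive different volumes from identical vials, so whoever gives the drug can infer the arm, which contradicts the stated blinding of data collectors

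*Combined protocol and SAP*

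**What the plan says.** The Study design section describes a "randomized, double-blind, placebo-controlled, parallel-group trial". Under Randomisation, an independent off-site pharmacist will "prepare and consecutively number identical study packages", and once consent is given "the research midwife will take the next sequentially labeled study drug package and administer its contents to the eligible participant". From this the section concludes that "both the participants and data collectors will remain blinded throughout the study".

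The Intervention/Comparator paragraph, directly below, gives the regimens as "100 mls (8.4g), 150 mls (12.6g) and 200 mls (16.8g) of 8.4% sodium bicarbonate solution, or placebo (50 mls of NS 0.9" (0.9% saline). Drug and saline "will be contained in identical 25 mL glass vials" and are "administered intravenously as a single bolus dose".

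On who collects the data, the Data collection section says "Our research assistants will be qualified midwives with training in data collection". There and under Study procedures, a research midwife monitors each woman for 24 hours and completes the questionnaire. Side effects are found by examination and by asking the woman. Sample collection quality control has research midwives drawing the blood. The Management section says that the study pharmacist will blind the drugs, but gives no method.

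**The concern.** Identical vials hide what is in a vial. They do not hide how many are used. If each arm needs a different number, the person who empties the package learns the arm, or can work it out after a few women.

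This matters most for safety, which is one of the two specific objectives. The Data analysis plan compares the incidence of side effects between arms as risk differences. The Adverse events/side effects paragraph lists 14 items. Four of them can largely be observed: leg swelling, venous irritation, slow breathing and cellulitis. The other ten depend mainly on what the woman reports or how the assessor judges it, for example thirst, nausea, tiredness, restlessness and mood. An assessor who knows that a woman received the largest volume may probe harder or record more.

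The same counts feed the rule, in the Independent Data Monitoring Committee section, that allows a halt when adverse events in an active arm reach 10% in comparison with placebo. Masking the groups in the committee's reports cannot repair data collected by staff who knew the arm.

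**Working it through.** **1. Are the printed volumes real?** Inputs from Intervention/Comparator: 8.4% solution (0.084 g/mL), the four volumes and 25 mL vials.

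| Arm | Volume (mL) | Grams = 0.084 × volume | Plan's grams | Vials = volume / 25 |
|---|---|---|---|---|
| Placebo | 50 | – | – | 2 |
| Low | 100 | 8.4 | 8.4 | 4 |
| Middle | 150 | 12.6 | 12.6 | 6 |
| High | 200 | 16.8 | 16.8 | 8 |

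The plan's gram figures reproduce exactly, so the bicarbonate volumes are not a misprint. The vial counts match the arms one to one. The plan does not state vials per package; the count follows from the division.

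**2. Who sees the count?** Randomisation and Study procedures have the research midwife administer the contents. Study procedures, Data collection and Sample collection quality control give the questionnaire, the 24-hour monitoring and the blood draws to the same role. No section assigns these tasks to different people.

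**3. Is there a masking step?** The text describes no equal fill, saline top-up, dummy vials, covered bag or line, or independent person to give the drug.

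**4. Does the budget imply one?** Using 118 women per arm (Sample size estimation), or 70 per arm before the final inflation:

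- Bicarbonate vials as written: 118 × (4 + 6 + 8) = 2,124, or 70 × 18 = 1,260. Budgeted: 2,000 units.
- Saline vials as written: 118 × 2 = 236, or 70 × 2 = 140. Budgeted: 100 units, described as the placebo.
- Saline vials if every arm were matched to 200 mL: 8 for placebo, then 4, 2 and 0, which is 14 for each set of four women. 118 × 14 = 1,652, or 70 × 14 = 980.

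The saline line shows no sign of volume matching. This is weak evidence, because unit size is not given. At one vial per unit, 100 units would not cover even the 140 placebo vials needed at 70 per arm.

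**5. How few reports could matter?** Suppose that the 10% rule means an absolute difference and is applied at the 140 women named under Interim analyses. That is 140 / 4 = 35 per arm and 0.10 × 35 = 3.5, so a net excess of four women would reach it. The plan does not say whether the 10% is absolute or relative, so this only shows the scale.

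**The case against.** The strongest reply is that masking may exist but be undescribed. The pharmacist is said to blind the drugs, and the flow diagram to which the text refers is not available in the version reviewed. That stands as a caution: the vial count is inferred, and it is not shown that every woman's arm would be known. However, any such step would still have to be squared with the four volumes in the text.

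It can also be said that the primary outcome is maternal pH read on a blood gas analyser, and that the largest difference in volume between arms, 200 − 50 = 150 mL, is small beside the 1.5 L of saline given to all. Both stand. The measured pH is largely protected. Volume does rise with dose, so the two cannot be separated, but this is a minor point.

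A reader might infer more than the documents support:

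- **The next package can be recognised before enrolment by size or weight.** Randomisation calls the packages identical and has them taken after consent. Size and weight are given nowhere.
- **The last allocation in a block of four is certain.** That needs a known block start and length, and sizes four, six and eight are mixed. Take only four and eight, equally likely, with a known start. Three different arms then occur first with probability 1 in a block of four and (6/7)(4/6) = 4/7 in a block of eight, so the chance that it is a block of four is 1 / (1 + 4/7) = 7/11. The missing arm comes next with probability 7/11 + (4/11)(2/5) = 43/55, or 0.78. With unknown starts it would be lower.
- **One midwife does everything.** The text says only that the role is shared. Four research assistants are budgeted for 24-hour coverage, so monitoring will probably cross shifts.
- **Knowing the arm changes the urgency of delivery.** No section gives that decision to the research midwife.
- **Participants are unblinded too.** A woman may see the volume without knowing what it means.

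**Conclusion.** The concern holds for the plan as written. Four volumes from identical 25 mL vials imply 2, 4, 6 or 8 vials, so the arm can be inferred by whoever gives the drug. The role that gives it also asks about side effects. The plan therefore does not deliver blinding of data collectors, and its double-blind label is unsupported for that role.

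The consequence falls mainly on side-effect ascertainment. The direction and size of any bias cannot be estimated from the documents, and analysis cannot restore blinding once it is lost. The conclusion assumes that the printed volumes are those given and that no undescribed masking step exists. It does not extend to a failure of allocation concealment or to an invalid primary pH comparison.

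**What to change.** Reconcile the volumes with the blinding statement, leaving the bicarbonate doses as they are. Any one of three routes would do.

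(a) The off-site pharmacist packs every numbered package with the same number of identical vials whose labels do not show content, given by the same procedure. Any common volume changes the fluid that women receive, so the clinical team must decide it. For costing only, matching to 200 mL takes 1,652 saline vials at 118 per arm. At the budget's USD 3 per unit, if one unit is one vial, that is 1,652 × 3 = USD 4,956, against 100 × 3 = USD 300 budgeted, or about 8% of the USD 60,000 total. At 70 per arm it is 980 × 3 = USD 2,940.

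(b) Within the existing midwife team, the midwife who opens and gives the package does not question that woman about side effects. Another midwife, unaware of the package contents, does so, and used vials and volume records are kept from her. Nothing need be bought, but checks are hourly for the first six hours, so the roster must allow a second midwife at that time. The label should then say that participants and side-effect assessors are blinded.

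(c) Remove the double-blind label and the statement on data collectors, and report side effects as assessed by staff who could know the arm. This costs only a text change, but it limits what the safety comparison can claim.

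If a masking method already exists, describe it in the Intervention/Comparator section.

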We will recruit 280 participants; 70 in each of the four arms. Wiberg-Itzel et al [2] observed mean umbilical artery pH 7.23 (SD 0.07) in the non-intervention group. With our sample size, we will have 80% power (significance level 0.05) to detect mean pH changes of 0.04 and above in each arm. We are interested in detecting an effect size of 0.2 and above, which we deem to be a moderate effect size. The total sample size needed to detect a between-factor mean effect size of 0.2, by repeated measures analysis of variance (ANOVA) with a type 1 error margin of 5%, across 4 groups with 5 repeated measurements; was 224 at a power of 91%. Assuming a 20% loss to follow up in our study; we will need 280 participants (70 in each of the 4 groups). The sample size was calculated using G* Power software version 3.1 using the test family for the F test, and the statistical test for ANOVA repeated measures, between factor analysis & within-between interaction [10]. Therefore, our sample size will also be sufficient to detect a within and between-subject interaction (intervention and time interaction) with a power of 99%. To obtain these estimates, we will construct an interaction term between the intervention and the time variable. We are confident that we shall be able to accrue this number of participants in a period of six calendar months, on the basis of our experience working in the same hospital [7]. In order to detect a change in maternal pH, a minimum of two measurements are needed from a participant. However, with improvement of obstetric care, many women deliver within 30 minutes of taking the baseline measurements and hence no second measurement is obtained. To account for this form of right censoring, we have inflated our sample size by 192 participants to ensure that we have at least 280 women with at least two pH measurements. We will recruit 472 participants; 118 in each of the four arms.

Outcome variables

The primary outcome measure will be the mean change in maternal pH from baseline in each group. The secondary outcomes will include, mean pH and lactate in maternal and umbilical blood, early neonatal death, safety (side effects) of sodium bicarbonate, primary PPH, sepsis and death. Furthermore, the plasma concentrations of HCO₃ levels will be measured as well to accurately estimate the required dose.

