Secondary outcomes will include neonatal death, postpartum haemorrhage and sepsis, in addition to the pharmacokinetics of sodium bicarbonate infusion in pregnant women. Details of measurements are in table 1.

The independent variables will include the sociodemographic, clinical, and obstetric characteristics of the study participants at different time points as indicated in table 1.

Table 1: Measurements to be taken from the participant samples

Activity/ procedure	Time in minutes							Comment
	Baseline (0)	30	60	90	120	150	At birth	
Metabolites (lactate & glucose)	X	X	X	X	X	X		Bedside using the RAPID Point 500e or YSTE-BG100 Blood gas analyzer
Blood gases (pH, pCO ₂ , pO ₂)	X	X	X	X	X	X	X	
Serum Electrolytes (Na ⁺ , K ⁺ , Ca ²⁺ , Cl ⁻)	X	X	X	X	X	X	X	
Umbilical cord blood for lactate							X	Bedside using the RAPID Point 500e or YSTE-BG100 Blood gas analyzer
Myometrial Lactate only collected at Caesarean section							X	Bedside using the RAPID Point 500e or YSTE-BG100 Blood gas analyzer
Creatinine	X							Total of 5 mL of venous blood will be taken to a central laboratory; these are part of the standard care for each patient.
Liver function tests (ALT&AST)	X							
Full blood count	X							
Amniotic fluid lactate*	X							Lactate Pro device
Bicarbonate concentrations in plasma	X	X	X	X	X	X	X	Bedside using the RAPID Point 500e or YSTE-BG100 Blood gas analyzer

[figure not shown]

Figure 2: Flow of participants in the trial from screening to analysis

Recruitment and data collection from participants

Participants: Obstructed labour will be diagnosed by either an obstetrician or medical officer using a definition of the American Association of Obstetricians and Gynaecologists (ACOG). In the first stage of labour, the participant should have cervical dilatation >6 cm with ruptured membranes, adequate contractions lasting >4 hours with no change in cervical dilatation or delay in the second active stage of labour (nullipara >2 hours, multipara >1 hour) with adequate uterine contractions. In addition, any two of: the obvious signs of severe obstruction such as caput formation, severe moulding, Bandl's ring, subconjunctival haemorrhages or an oedematous vulva.

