short turnaround time on blood results to inform clinical decision making. In the event of system downtime, we will use a YSTE-BG100 Blood Gas Analyzer (Yuesen Med, China) as a backup. The YSTE-BG100 is a compact and user-friendly device that can rapidly assess key parameters including pH, lactate, glucose, electrolytes, and blood gases [17], thereby ensuring continuity of care even when the RAPIDPoint® 500e Blood Gas System is down. In our previous trial the study drug was sourced from the local supplier accredited by the National Drug Authority (NDA). We intend to use 8.4% sodium bicarbonate (intervention), and sodium chloride 0.9% (placebo) from NEON laboratories Ltd, Mumbai, India.

Adverse events/side effects: Based on the package insert labelling for sodium bicarbonate and a review of the literature [18], we will actively monitor for the following; increased thirst, continuing loss of appetite, swelling of the lower limbs, venous irritation, muscle pain or twitching, continuing headache, nausea or vomiting, stomach cramps, unusual tiredness or weakness, nervousness or restlessness, mood or mental changes, frequent urge to urinate, slow breathing and cellulitis at the injection site. This will be done hourly for the first six hours, six hourly for the next 18 hours and then daily throughout the period of hospitalization.

Follow-on plan

We plan to publish our results in a peer reviewed journal irrespective of the findings, as we have demonstrated in the past. Furthermore, we have established contact with [name] in Oslo to advise on the setup of our current study. His group is undertaking similar work (<https://ichgcp.net/clinical-trials-registry/NCT05719467>), and they could be potential collaborators on a larger grant application if the results are positive (see attached support letter). We have a community advisory group that is crucial in disseminating our findings to the lay public. [name] is also a member of National Safe Motherhood Executive Committee (NASMEC), a ministry of health technical advisory group on maternal health. He will disseminate the findings in this group.

Table 2: Proposed study timelines

Activity	2024												2025					
	Jan	Feb	Mar	Apr	May	Jun	Jul	Aug	Sep	Oct	Nov	Dec	Jan	Feb	Mar	Apr	May	Jun
REC & UNCST approvals	*	*	*	*	*													
Recruitment of staff					*	*	*											
Procurements		*	*	*	*	*	*	*	*	*	*							
Data collection							*	*	*	*	*	*	*	*	*	*	*	*
Data analysis											*	*	*	*	*	*	*	*

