Dissemination and Publications															*	*	*	*

Pharmacokinetics of sodium bicarbonate

Study design: This will be a population-based pharmacokinetics study of sodium bicarbonate using plasma levels in pregnant women with obstructed labour. We propose to investigate the association between the exposure of various doses of sodium bicarbonate (i.e. 8.4g, 12.6g and 16.8g) in pregnant women with obstructed labour, and identify determinants to inform dosing policy guidelines.

Study population: We will establish a cohort of pregnant women with obstructed labour in Mbale regional referral hospital. Only mothers that consent to participate in the study will be included.

Data collection: Following the administration of sodium bicarbonate, a blood sample will be collected from the mother at time 30, 60, 90, 120 and 150 minutes and at the time of childbirth; and then umbilical cord blood will be collected at birth for testing. Consequently, the concentrations of sodium bicarbonate will be determined using liquid chromatography (HPLC) method with electrochemical detection as described by Rodriguez [19]. The HPLC analysis will be conducted at Busitema University Ministry of Science, Technology and Innovation supported laboratory. Data from the respective participants will include PK, socio-demographics, adverse events and other clinical parameters including weight and age.

Data analysis: Non-compartmental analysis will be used to analyse the intensive PK data for sodium bicarbonate and a population pharmacokinetic model will be developed to analyse the sparse PK data. Any disparate treatment approached, additional medications or relevant clinical information, will be captured and adjusted for in the model. We will use nonlinear mixed-effects modelling (also known as population PK) to interpret the sodium bicarbonate pharmacokinetic data and assess the effect of variation. PopPK modelling offers a semi-mechanistic platform to interpret PK data, in that it evaluates the effect of patient covariates on physiological PK parameters (such as clearance and bioavailability), as opposed to hydroxyurea concentrations summary values (such as AUC and C_{max}). The concentration-time data for the drugs of interest will be analysed using popPK (nonlinear mixed-effects) modelling in NONMEM.

References

1. Wray S: **Insights into the uterus**. *Experimental Physiology* 2007, **92**(4):621-631.

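### Two sections end maternal pH sampling at delivery and add 192 women for the lost values, while Table 1 and the pharmacokinetics section already schedule a second maternal sample for early deliverers

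*Combined protocol and SAP*

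**What the plan says.** - **Outcome variables:** "The primary outcome measure will be the mean change in maternal pH from baseline in each group". Nothing restricts this to the time before birth. The Data analysis plan words the primary outcome more widely, as acidosis measured by pH and lactate.
- **Sample size estimation and sampling:** "In order to detect a change in maternal pH, a minimum of two measurements are needed from a participant". It then says that "many women deliver within 30 minutes of taking the baseline measurements and hence no second measurement is obtained", and "To account for this form of right censoring, we have inflated our sample size by 192 participants". The total becomes 472, or 118 per arm.
- **Data collection:** laboratory parameters are "measured at baseline, and every thirty minutes after study drug administration until delivery".
- **Table 1:** the row that begins "Blood gases (pH, pCO ₂ , pO ₂" is marked at 0, 30, 60, 90, 120 and 150 minutes and at birth, with no note that the timed series ends at delivery. The lactate and glucose row has the same timed marks but none at birth.
- **Pharmacokinetics of sodium bicarbonate, Data collection:** "a blood sample will be collected from the mother at time 30, 60, 90, 120 and 150 minutes and at the time of childbirth".
- **Appendix 1, part F:** maternal pH has rows from 0 to 150 minutes and no row for birth.
- **Data analysis plan:** analysis is by intention to treat with repeated measures ANOVA. There is no rule for women without a second pH.

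**The concern.** Birth ends the pregnancy, not the mother's pH. A value that could be measured after delivery but is not taken is missing because of the sampling rule; it is not censored. Under the rule in the Data collection and sample size sections, a woman enters the primary comparison only if she is still undelivered when the next sample falls due. That depends on time to delivery, which comes after randomisation, so the analysed women would be a selected subset inside an analysis described as intention to treat.

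The selection matters most if time to delivery differs by arm. The documents do not say that it does, but it cannot be ruled out. The treatment is meant to act on the fetus while caesarean section is awaited. The arms also receive 50, 100, 150 or 200 mL from 25 mL vials, that is 2, 4, 6 or 8 vials, so staff might infer the allocation. Extra recruitment restores the number of evaluable women, not the comparability of the arms.

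Two further things are at stake. Of the 192 added women, 192 × 3/4 = 144 would be allocated to active drug. The rule also cuts off late samples: the Introduction says the earlier trial's lactate effect showed only after more than an hour, and the Intervention section gives an average wait for caesarean of about 110 minutes, before the 120- and 150-minute samples.

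**Working it through.** **1. The plan's own chain** (inputs from Sample size estimation and sampling).
- Loss to follow-up: 224/(1 − 0.20) = 280, as stated.
- Inflation: 280 + 192 = 472 and 472/4 = 118 per arm, as stated.
- Implied share without a second pH: 192/472 = 40.7%. Check: 280/(1 − 192/472) = 472.
- Power, repeated measures ANOVA, between factors: λ = N f² m/(1 + (m − 1)ρ), with 3 and N − 4 degrees of freedom. With N = 224, f = 0.2, m = 5 and ρ = 0.5 (assumed; the documents give no correlation), λ = 224 × 0.04 × 5/3 = 14.9 and power is 91.1%, against the stated 91%. Over ρ from 0.3 to 0.8, power runs from 97.5% to 78.2%.

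The arithmetic reproduces. The difficulty is the premise behind the 192.

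**2. The two accounts side by side, for a woman who delivers 20 minutes after dosing.**
- Sample size and Data collection sections: baseline pH only, so she falls below the two-measurement minimum.
- Table 1 and pharmacokinetics section: baseline plus a sample at birth, and timed samples to 150 minutes with no stated stop. She meets the minimum.

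Both cannot be followed. The clocks differ too: the sample size section counts 30 minutes from the baseline measurement, the Data collection section from study drug administration.

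**3. Where the 40.7% could come from.** No section gives the proportion delivering within 30 minutes. The nearest figure is the 110-minute average wait for caesarean. If waits were exponential with that mean (an assumption, for illustration), 1 − exp(−30/110) = 23.9% would deliver by 30 minutes. The total is sensitive to this share:

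| Share without a second pH | N for 280 with two values |
|---|---|
| 0% | 280 |
| 10% | 280/0.90, rounded up to 312 |
| 20% | 280/0.80 = 350 |
| 30% | 280/0.70 = 400 |
| 40.7% | 472 |

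The 280 already contains the 20% loss allowance. If lacking a second pH were the only loss, 224/(1 − 0.4068), rounded up to 378, would do.

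**4. What short series cost.** The 91% assumes five measurements. With two, λ = 224 × 0.04 × 2/1.5 = 11.9 and power is 83.1% (same ρ). Ending the series at delivery therefore affects later deliverers as well.

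**The case against.** The strongest reply is that Table 1 and the Data collection section can be read together: half-hourly samples while undelivered, with birth as the last draw. That is a fair reading, and Table 1's silence about stopping does not prove that post-birth samples were intended. It still gives every early deliverer a second pH at birth, so the statement that no second measurement exists remains in conflict.

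A second reply is that the aim is to improve acidosis while awaiting caesarean, so pH before birth is the natural target, and post-birth pH also reflects the end of contractions, surgery, blood loss and fluids. This stands in part. Pre-birth pH is a defensible estimand, but the plan does not name it or defend the selected subset that it brings. Nor is the added variation certain to be equal across arms: if dose changes the timing of birth, post-birth values carry that too.

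Third, post-birth sampling costs more than a wording change. The observation described by "This will be done hourly for the first six hours" is for side effects, not blood.

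Some stronger readings are tempting but unsupported.
- A reader might infer that 41% of randomised women will have no post-dose pH. That share is implied by the inflation, not observed or stated, and the at-birth sample contradicts it.
- A reader might infer that the comparison is biased by a known amount. No document gives time to delivery by arm, or how pH change differs between early and late deliverers, so no size can be derived.
- A reader might infer a 23% smaller standard error from sampling everyone, since 1 − √(280/472) = 0.23. That supposes no added variance after birth and no other losses, and is at best an illustration.

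**Conclusion.** The point holds as an internal conflict with a design consequence. The sample size and Data collection sections cannot be reconciled as written with Table 1 and the pharmacokinetics section, and delivery does not censor maternal pH. Applied as written, the first pair would select the primary analysis set on an event after randomisation. That is a risk of bias, conditional on time to delivery differing by arm, and not a demonstrated bias.

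The firm size is the 192 women, whose need rests on an unsupported 40.7%. If each woman has a second pH, the plan's own calculation returns to 280. This takes the plan's effect size, its 20% loss and ρ = 0.5 as given. It also takes Table 1's blood-gas mark at birth as maternal, which fits the separate row for cord blood and the maternal draw at childbirth in the pharmacokinetics section. For lactate the birth mark is absent, so a second maternal lactate in early deliverers depends on keeping the timed samples after birth. The matter should be settled before further sampling, because samples not taken cannot be recovered in analysis.

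**What to change.** 1. Reconcile the sample size section, Table 1, the Data collection section and the pharmacokinetics section. State that the maternal at-birth pH is taken in every woman and counts as a post-baseline value, and that the listed 30- to 150-minute samples continue after delivery where feasible. Use one clock.
2. Record each sample's actual time and whether it came before or after birth. Give the data form a clear field for maternal pH at birth.
3. Include all randomised women with any post-baseline pH in the intention-to-treat analysis, using a mixed model that accepts incomplete series and actual times. Report the pre-birth-only analysis alongside it, say in advance which estimand is primary and why, and report the number without a post-baseline pH by arm.
4. Re-justify the 192 with an observed share delivering before a second sample, or restate the total.

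**Cost.** The analyser needs 100 microlitres per sample and midwives monitor participants for 24 hours, but draws around surgery are a real burden. The budget lists cartridges for 290 participants. The consent description in Study procedures covers specimens taken in labour and may need a small change. Post-birth values also mix in the effects of delivery, surgery and fluids, which is why both analyses should be shown. This version is dated September 2025, after the data collection period in Table 2. If recruitment has begun (an inference), record which sampling rule applied to each woman.
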